10.2.2 Hepatic Toxicity

No dose interruption or dose modifications are required for Grade ≤ 2 transient hepatic toxicity. Increases in bilirubin and transaminases are routinely seen with this IC, and are usually quickly resolved within 2-3 days of completing (or stopping) hu14.18-IL2 treatment. Grade 3 toxicity will require cessation of agent and treatment at 50% dose when toxicity has resolved and entry criteria are met.

10.2.3 Cardiac toxicity and/or dyspnea

10.2.3.1 Cardiac abnormalities

Any evidence of cardiac abnormalities will require an immediate ECG evaluation. Evidence of ischemia will require immediate discontinuation of therapy. Subjects with evidence of asymptomatic atrial irregularities (including supraventricular tachycardia) related to an elevated temperature but no evidence of ischemia or clinically significant hypotension will be monitored but continue therapy.

10.2.3.2 Blood pressure and fluid overload

10.2.3.2.1 Fluid overload

Complications of fluid overload may be seen with IC treatment. Patients with clinical problems related to fluid overload can be treated with furosemide (20 mg IV) provided they have < 40 mm Hg decrease in systolic blood pressure from day 1 of cycle, obtained prior to initiation of IC therapy, and a systolic BP > 90 mm Hg.

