10.2.3.2.2 Hypotension

Mild hypotension with systolic blood pressure 10-15% below baseline is common in patents receiving IL2.

- a. Asymptomatic patients with mild hypotension should be monitored closely
- b. Symptomatic patients or those with systolic blood pressure < 85 mmHg or < 100 mmHg if representing a decrease in systolic blood pressure $> 20\%$ from the lowest value of any documented systolic blood pressure obtained since study consent was signed should be treated for hypotension. (Do not include blood pressures obtained on days of hu14.18-IL2 treatment after hu14.18-IL2 infusion started for purposes of getting this lowest usual blood pressure).

Patients meeting the above guidelines should be given a 500 ml IV bolus of normal saline over 15 minutes. If unresponsive:

- Stop the hu14.18-IL2 infusion
- Repeat the fluid bolus: 500 ml IV bolus of normal saline over 15 minutes. Fluid bolus may be repeated once or twice as needed. May be limited by symptomatic fluid overload (i.e. pulmonary edema, tense ascites).
- If unresponsive to fluid bolus, may give Albumin (25%) 50 gm IV, then q 6-12 h PRN if serum albumin ≤ 3.0 .
- RBC Transfusion to maintain Hgb ≥ 10.0 g/dL
- If responsive, (i.e., blood pressure increases to a systolic blood pressure over 100 mm Hg or to the patient's blood pressure prior to administration of hu14.18-IL2 for that day if the baseline systolic blood pressure was less than 100 mm Hg), may reinitiate the hu14.18-IL2 treatment on the following day (if scheduled) at

50% reduced dose. If hypotension is recurrent, treatment will be stopped and patients managed as outlined above in this section. Treatment can be restarted (at their next scheduled infusion day) at 25% of the initial dose, if systolic blood pressure is responsive to the fluid management described above. If hypotension is recurrent at this 25% dose, treatment will be discontinued and the patient will be off protocol therapy.

c. Symptomatic hypotension that does not respond to these measures requires:

- IV vasopressors, (i.e., phenylephrine, dopamine, etc.)

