10.2.3.4 Dyspnea

Subjects experiencing dyspnea and whose oxygen saturation is less than 90% may receive brief oxygen supplementation. Subjects who experience this toxicity are often fluid overloaded and will need furosemide, provided that they are not hypotensive (see management of hypotension, above). Therapy will be discontinued and not restarted until the oxygen saturation is above 90% without oxygen supplementation. Once the oxygen saturation is above 90% without oxygen supplementation, treatment with hu14.18-IL2 may be reinitiated on the following day (if scheduled) at 100% dose (if recovery occurred in less than 1 hour) or at 50% reduced dose (if recovery took longer than 1 hour to resolve). If they are fluid overloaded, hypoxic and hypotensive, treatment should be stopped and vasopressor support initiated, as needed. Once toxicities resolve, subsequent treatment will be at the 50% dose level.

If dyspnea with oxygen saturation below 90% is recurrent, treatment will be stopped and patients managed as outlined above in this section. Treatment can be restarted (at their next scheduled infusion day) at 50% of the prior dose, if oxygenation is responsive to the management described above. If dyspnea with oxygen saturation below 90% is recurrent at 25% of the initial dose, treatment will be discontinued and the patient will be off protocol therapy.

If the oxygen saturation does not then improve to over 90% off of oxygen supplementation within 24 hours, treatment will be discontinued and restarted at 50% of the previous dose of

hu14.18-IL2, provided that the toxicity resolves. If they are fluid overloaded, hypoxic and hypotensive, treatment should be stopped and vasopressor support initiated, as needed. Once toxicities resolve, subsequent treatment will be at the 50% dose level.

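### The fluid-overload and hypotension rules overlap: a fluid-overloaded subject at 91–99 mm Hg systolic can, depending on reference pressures, be permitted furosemide and directed to a 500 ml saline bolus at once

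*Combined protocol and SAP*

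**What the plan says.** Three neighbouring paragraphs of the toxicity-management section deal with fluid and pressure.

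- **Section 10.2.3.2.1 (Fluid overload)** permits "furosemide (20 mg IV) provided they have < 40 mm Hg decrease in systolic blood pressure from day 1 of cycle", the day 1 reading being the one "obtained prior to initiation of IC therapy, and a systolic BP > 90 mm Hg". So there are two conditions: a limit on the fall from day 1, in mm Hg, and a floor on the current pressure.
- **Section 10.2.3.2.2 (Hypotension)** covers symptomatic patients and those with "systolic blood pressure < 85 mmHg or < 100 mmHg if representing a decrease in systolic blood pressure" of more than 20%, measured "from the lowest value of any documented systolic blood pressure obtained since study consent was signed should be treated for hypotension". Readings taken after the infusion has started on a treatment day do not count toward that lowest value. The action is: "Patients meeting the above guidelines should be given a 500 ml IV bolus of normal saline over 15 minutes". Fluid overload appears only in the bullet on repeating the bolus, after the first has failed: "May be limited by symptomatic fluid overload (i.e. pulmonary edema, tense ascites".
- **Section 10.2.3.4 (Dyspnea)** opens with its scope: "Subjects experiencing dyspnea and whose oxygen saturation is less than 90% may receive brief oxygen supplementation". Such subjects, often fluid overloaded, "will need furosemide, provided that they are not hypotensive (see management of hypotension, above". For those who are overloaded, hypoxic and hypotensive together, it says to stop treatment and use vasopressors as needed.

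The first two paragraphs do not refer to each other.

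**The concern.** The two rules under 10.2.3.2 use different absolute limits, different reference pressures and different measures of fall (mm Hg against percent). One permits a diuretic; the other directs fluid. If the same subject can satisfy both, the protocol gives opposing guidance for fluid overload with low pressure. The protocol expects that setting: 10.2.3.2.1 anticipates fluid overload with this agent, and 10.2.3.3 describes capillary leak with edema under high-dose IL2.

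The choice of paragraph also bears on study drug. Under 10.2.3.2.2 a failed first bolus stops the infusion, and recurrences lead through 50% and 25% of dose to discontinuation. Section 10.2.3.2.1 contains no such steps. The dose a subject receives could therefore depend on which paragraph staff apply.

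**Working it through.** The plan gives no figure to reproduce. The check is whether the conditions can hold together.

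**Inputs.** Let x be the current systolic pressure, D the day 1 pressure before infusion (10.2.3.2.1), and L the lowest documented pressure since consent (10.2.3.2.2). The day 1 pre-infusion reading itself counts toward L, so L ≤ D.

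**Rules.**
- Furosemide permitted: x > 90 and D − x < 40.
- Bolus directed by pressure: x < 85, or x < 100 with (L − x)/L > 0.20. The second form is the same as L > x/0.8 = 1.25x.

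**Overlap by pressure.** The limb below 85 can never meet the floor above 90. The other limb gives 90 < x < 100 and 1.25x < L ≤ D < x + 40. Subtracting the bounds, D − L must be under 40 − 0.25x.

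| x (mm Hg) | L must exceed | D must be below | D − L must be under |
|---|---|---|---|
| 91 | 113.75 | 131 | 17.25 |
| 95 | 118.75 | 135 | 16.25 |
| 99 | 123.75 | 139 | 15.25 |

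Enumerating whole-number pressures gave solutions at every x from 91 to 99 and at no other value.

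**Example.** L = 120, D = 125, x = 95.
- Fall from L: (120 − 95)/120 = 20.8%, above 20%, and 95 < 100, so the bolus is directed.
- Fall from D: 125 − 95 = 30 mm Hg, under 40, and 95 > 90, so furosemide is permitted if the subject is overloaded.

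**Overlap by symptoms.** The symptomatic limb of 10.2.3.2.2 states no upper pressure. A symptomatic, overloaded subject meets both rules whenever x > 90 and D < x + 40, whatever L is. At x = 100, for instance, D need only be below 140. The 91–99 range is therefore not the whole overlap.

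**Adding Section 10.2.3.4.** Suppose the example subject also has dyspnea with saturation below 90%. The falls are 20.8% from L and 30/125 = 24% from D. The subject meets the treatment trigger in 10.2.3.2.2, and the fall is also beyond the 10–15% which that section calls mild hypotension. On either reading the subject is hypotensive. Section 10.2.3.4 then withholds the furosemide that 10.2.3.2.1 permits. It also points to stopping treatment and vasopressors as needed, whereas 10.2.3.2.2 stops the infusion only after the first bolus fails and reaches vasopressors later still.

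**The case against.** **A permission is not an order.** Section 10.2.3.2.1 says furosemide can be given; 10.2.3.2.2 says the bolus should be given. Staff who give the bolus and leave the permission unused comply with both. A reader might infer that the three sections cannot all be followed; the wording does not support that. What stands is that the text permits one action and directs the opposite one in the same subject, without saying which governs.

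**Section 10.2.3.4 is narrow.** A reader might infer that it bars furosemide in every overlapping subject. It does not: it covers only dyspnea with saturation below 90%, and for overloaded, hypoxic and hypotensive subjects it has its own instruction. Overloaded subjects without that hypoxia are left with the unresolved pair.

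**The overlap is conditional.** A pressure of 91–99 mm Hg is not enough by itself. If L lies about 15 to 17 mm Hg or more below D, the pressure overlap disappears. In the example, an earlier reading of 118 instead of 120 makes the fall 23/118 = 19.5%, and the pressure trigger is not met. This stands as a limit on size, but the qualifying pressures in the table are still a usable range.

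**A reverse conflict at 85–90 mm Hg.** A reader might argue that a subject at 88 from 108 (20/108 = 18.5%) is not hypotensive, so 10.2.3.4 calls for furosemide while 10.2.3.2.1 refuses it. This does not hold as stated. The 20% rule says who should be treated, not who is hypotensive, and the same section calls a 10–15% fall mild hypotension. The argument also needs hypoxia, and a dyspneic subject who does not count as symptomatic.

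**Supervision.** Infusions are given in hospital under close observation (8.1.2.8), so clinical judgment will often settle the matter. That reduces the risk without making the text consistent.

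**Conclusion.** The point holds as an internal inconsistency in a safety rule. Sections 10.2.3.2.1 and 10.2.3.2.2 overlap at every whole-number systolic pressure from 91 to 99 mm Hg when L > 1.25x and D < x + 40, and at higher pressures for symptomatic subjects. The fluid-overload caveat does not reach the first bolus. In subjects who also have dyspnea with saturation below 90%, 10.2.3.4 withholds what 10.2.3.2.1 permits, reading *hypotensive* through its cross-reference to the hypotension section.

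How often this would arise cannot be computed from the documents. In Phase I at 6.0 mg/m², Table 2 shows Grade 2 hypotension in 2 of 6 subjects in course 1 and 1 of 3 in course 2. The table has no fluid-overload row, so these counts show that low pressure occurs, not that the overlap does.

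A reader might also infer that the choice of paragraph shifts the counts in the Section 9.4.9 stopping rule. The documents do not support that. The suspension thresholds count Grade 4 events, the Phase I report describes no Grade 4 toxicities, and nothing traces a path from this choice to a Grade 4 count. No power figure, error rate or stopping boundary changes.

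**What to change.** Reconcile Sections 10.2.3.2.1, 10.2.3.2.2 and 10.2.3.4. Give *hypotensive* one meaning across the three, and state which paragraph governs when fluid overload and low pressure coexist, with and without hypoxia. In doing so, make clear whether the fluid-overload caveat applies to the first bolus. The pressure limits, reference readings and actions are for the sponsor's clinicians to set. The cost is protocol wording; sample size, data collection and analysis are unaffected.

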10.2.3.2.2 Hypotension

Mild hypotension with systolic blood pressure 10-15% below baseline is common in patents receiving IL2.

- a. Asymptomatic patients with mild hypotension should be monitored closely
- b. Symptomatic patients or those with systolic blood pressure < 85 mmHg or < 100 mmHg if representing a decrease in systolic blood pressure $> 20\%$ from the lowest value of any documented systolic blood pressure obtained since study consent was signed should be treated for hypotension. (Do not include blood pressures obtained on days of hu14.18-IL2 treatment after hu14.18-IL2 infusion started for purposes of getting this lowest usual blood pressure).

Patients meeting the above guidelines should be given a 500 ml IV bolus of normal saline over 15 minutes. If unresponsive:

- Stop the hu14.18-IL2 infusion
- Repeat the fluid bolus: 500 ml IV bolus of normal saline over 15 minutes. Fluid bolus may be repeated once or twice as needed. May be limited by symptomatic fluid overload (i.e. pulmonary edema, tense ascites).
- If unresponsive to fluid bolus, may give Albumin (25%) 50 gm IV, then q 6-12 h PRN if serum albumin ≤ 3.0 .
- RBC Transfusion to maintain Hgb ≥ 10.0 g/dL
- If responsive, (i.e., blood pressure increases to a systolic blood pressure over 100 mm Hg or to the patient's blood pressure prior to administration of hu14.18-IL2 for that day if the baseline systolic blood pressure was less than 100 mm Hg), may reinitiate the hu14.18-IL2 treatment on the following day (if scheduled) at

50% reduced dose. If hypotension is recurrent, treatment will be stopped and patients managed as outlined above in this section. Treatment can be restarted (at their next scheduled infusion day) at 25% of the initial dose, if systolic blood pressure is responsive to the fluid management described above. If hypotension is recurrent at this 25% dose, treatment will be discontinued and the patient will be off protocol therapy.

c. Symptomatic hypotension that does not respond to these measures requires:

- IV vasopressors, (i.e., phenylephrine, dopamine, etc.)
- If responsive (i.e., blood pressure increases to a systolic blood pressure over 100 mm Hg or to the patient's blood pressure prior to administration of hu14.18-IL2 for that day if the baseline systolic blood pressure was less than 100 mm Hg and no longer requiring vasopressor support), may reinitiate the following day (if scheduled) at 50% reduced dose. If hypotension is recurrent, treatment will be stopped and patients managed as outlined above in this section. Treatment can be restarted (at their next scheduled infusion day) at 25% of the initial dose, if systolic blood pressure is responsive to the fluid management described above. If hypotension is recurrent at this 25% dose, treatment will be discontinued and the patient will be off protocol therapy.
- For Grade 3 hypotension, see dose modification guidelines in section 10.1
- Additional boluses of 500 ml IV Normal Saline can be administered as clinically indicated

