The above dose limiting toxicity exceptions are based on the known, published, transient, reversible toxicities of IL2 and hu14.18. These toxicities may be expected, based on observations of hu14.18-IL2 given to 33 + 14 (phase I and II respectively) adults with melanoma, administered by the same schedule at similar doses to that being tested in this trial, and will not require interruption, modification, or discontinuation of treatment. In our experience with hu14.18-IL2 in adults with melanoma, asymptomatic hypophosphatemia is a relatively frequent occurrence. Therefore, all subjects scheduled to receive this agent will be given oral phosphate supplementation prophylactically starting on day 1 and ending on day 8 of each course (see Section 10.3.4.3 for details). **All grade 4 toxicities (except for transient lymphopenia) are considered as DLT and require stopping treatment with hu14.18-IL2. Following resolution of a DLT, and if subsequent hu14.18-IL2 treatment is given, it must be given at a reduced dose.**

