5.4.4.1 Dose-reduction plan for hu14.18-IL2

For toxicity associated with hu14.18-IL2, there must also be consideration of the schedule of administration. If this toxicity occurs on day 1 or 2 of any course, treatment can be resumed during that same course (i.e., on day 2 or 3) at 50% of the starting dose only if the toxicity has improved to meet eligibility criteria in time to give the day 2 or day 3 dose on schedule. If eligibility criteria are not met in time to receive additional therapy during the course in which the toxicity occurred, but are met in time to start the next course (i.e., day 1 of the next course +/- 7 days), treatment will resume at 50% of the dose that caused the DLT. If toxicity again requires treatment cessation, treatment can be restarted at 25% of initial treatment dose. If treatment at this reduced dose results in recurrence of DLT or significant non-DLT toxicity, treatment will be permanently discontinued.

Repeat lab testing will be done weekly until eligibility criteria are met, and treatment will begin at 50% of the prior dose. If after 4 additional weeks of testing, eligibility criteria still are not met, the subject will not be eligible for any additional treatment with the study agent responsible.

Subjects with Grade 4 toxicity related to protocol treatment (other than transient lymphopenia from hu14.18-IL2, see Section 5.3.3.g) will not receive additional protocol treatment during that treatment course. Patients experiencing Grade 4 neutropenia or leukopenia that lasts \leq 4 days; Grade 4 thrombocytopenia that can be corrected with platelet transfusion (see Section 10.2.1); or Grade 4 nausea, vomiting, anorexia or fatigue lasting less than 2 days, and resolves to meet eligibility criteria, may be eligible to receive continued study therapy (provided that all other criteria for continued treatment are met) at 50% of the dose received prior to the onset of this toxicity. Subjects with any other Grade 4 toxicity related to the protocol treatment will not receive additional protocol treatment during that course and will be withdrawn from the study. Subjects experiencing Grade 4 events that are clearly unrelated to the study treatment, last \leq 3 days, and improve to meet eligibility criteria, may be eligible to receive continued study therapy (provided that all other criteria for continued treatment are met) at 50% of the daily dose received prior to the onset of this toxicity.

[figure not shown]

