³ The “yes” or “no” will be based on the FDA’s decision after consulting with them on a case-by-case basis, both at the time of onset and time of resolution of the toxicity.

⁴ If this is the first time the DLT was noted, reduce dose to 50% of starting dose. If this is the second time the DLT was noted, reduce to 25% of starting dose. If this is the third time, treatment must stop—no further dose reductions are allowed.

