10.1.1 Dose modification for DLT

Dose limiting Toxicity (DLT) criteria and exclusions are described in protocol section 5.3. For any occurrence of DLT, treatment with protocol therapy will be stopped. Treatment may not be resumed until after toxicity has resolved to meet original eligibility criteria. Resuming treatment following any DLT at a reduced dose (according to the guidelines below) requires contact (by phone or e-mail) with the FDA on a case-by-case basis. The first contact will be to the FDA Oncology Drug Products review division in the Center for Drug Evaluation and Research at [contact]. An alternate contact is at the following: [contact]; [contact], [contact].

For toxicities occurring during treatment with hu14.18-IL2, if DLT occurs on day 1 or 2 of any course, treatment can only be resumed during that same course (i.e., on day 2 or 3) at 50% of the starting dose, and only if the toxicity has resolved to meet eligibility criteria in time to give the day 2 or day 3 dose on schedule. If eligibility criteria are not met in time to receive additional therapy during the course in which the toxicity occurred, but are met in time to start the next course (i.e., day 1 +/- 7 days), treatment will resume at 50% of the dose associated with the DLT. Any planned drug administration that is withheld due to DLT will not be given on a delayed schedule to “make up” for missed drug. If toxicity again requires treatment cessation, treatment can be restarted at 25% of initial treatment dose. If treatment at this reduced dose results in recurrence of DLT or significant non-DLT toxicity, treatment will be permanently discontinued. Treatment will be resumed, as described above, using only 50% of the starting dose of hu14.18-IL2, and only if the toxicity has resolved to meet eligibility criteria.

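### Section 10.2.3.2.2(c) permits a next-day half-dose restart after vasopressor-treated hypotension without excluding Grade 4, for which 5.4.4.1 requires no more drug in that course and withdrawal when treatment-related

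*Combined protocol and SAP*

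**What the plan says.** Section 10.2.3.2.2(c) covers symptomatic hypotension that persists after fluids and the other supportive measures and is then treated with vasopressors. If the pressure recovers and support is off, the drug "may reinitiate the following day (if scheduled) at 50% reduced dose", with a further step to 25% of the initial dose if hypotension recurs. One grade is named: "For Grade 3 hypotension, see dose modification guidelines in section 10.1".

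Section 5.4.3 states: "All grade 4 toxicities (except for transient lymphopenia) are considered as DLT and require stopping treatment with hu14.18-IL2". Section 5.4.4.1 adds that subjects with related Grade 4 toxicity, transient lymphopenia aside, "will not receive additional protocol treatment during that treatment course". It lists exceptions that may later continue at 50%: short neutropenia or leukopenia, thrombocytopenia correctable by transfusion, and "Grade 4 nausea, vomiting, anorexia or fatigue lasting less than 2 days". Subjects with any other related Grade 4 toxicity "will not receive additional protocol treatment during that course and will be withdrawn from the study". A separate provision lets clearly unrelated Grade 4 events lasting 3 days or less continue at 50%.

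Section 10.1.1 repeats the general day 2 or 3 restart at 50% and adds a safeguard: "Resuming treatment following any DLT at a reduced dose (according to the guidelines below) requires contact (by phone or e-mail) with the FDA". A surviving footnote to the figure in 5.4.4.1 rests a yes/no step on the FDA's "decision after consulting with them on a case-by-case basis, both at the time of onset and time of resolution of the toxicity".

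**The concern.** Section 10.2.3 is what ward staff would consult during an acute hypotensive episode. Read alone, (c) gives them a route back to dosing the next day whatever the grade. The rule that closes that route for related Grade 4 events sits in another chapter, and (c) does not cite it. At stake is re-exposing a subject to the agent after an event that the protocol treats as grounds for withdrawal. This is a subject-safety and internal-consistency point. It does not bear on the statistical design.

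**Working it through.** No plan figure is in dispute, so the check is mainly a comparison of provisions.

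**Step 1. Does Grade 4 hypotension fall within (c)?** Yes. Section 9.4.9 counts Grade 4 hypotension among the unacceptable toxicities that require vasopressors, and vasopressor treatment is what (c) describes.

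**Step 2. Is all vasopressor-treated hypotension Grade 4?** No. Section 1.3.5 reports two Phase I subjects with Grade 3 hypotension, one of whom did not need pressors, which implies that the other did. That trial cites the NCI Common Toxicity Criteria, not the CTCAE 3.0 used here. So (c) has a legitimate use below Grade 4.

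**Step 3. What does each provision direct for a related Grade 4 hypotension on day 1 or 2, off vasopressors by the next day?**

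| Provision | Direction | Grade limit |
|---|---|---|
| 10.2.3.2.2(c) | May restart next day at 50% | None; only Grade 3 is pointed elsewhere |
| 5.4.3 | Stop; it contemplates later treatment at a reduced dose once the DLT resolves | Every Grade 4 except transient lymphopenia |
| 5.4.4.1 | No more drug in that course; withdraw unless excepted | Related Grade 4; hypotension is not an exception |
| 10.1.1 | Day 2 or 3 restart at 50% if eligibility criteria are met; FDA contact first | None stated |

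The same-course bar and the withdrawal therefore come from 5.4.4.1. Section 5.4.3 supplies the stop and the DLT status.

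**Step 4. Does the pointer to 10.1 close the gap?** For Grade 3 it leads to the FDA-contact rule. For Grade 4 there is no pointer. A reader who goes to 10.1.1 anyway finds the general restart rule that also opens 5.4.4.1, without the Grade 4 paragraph that follows it there. Its reference for DLT criteria is to 5.3, although they now stand in 5.4. The eligibility condition does not screen blood pressure directly, because Section 3 sets no blood-pressure threshold.

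**Step 5. How often could this arise?** With zero events in n subjects, the one-sided 95% upper bound is 1 − 0.05^(1/n).
- Phase I, any Grade 4 toxicity, 0 of 33 (doses 0.8 to 7.5 mg/m²/day): 1 − 0.05^(1/33) = 0.087.
- Phase II at 6 mg/m²/d, protocol-defined DLT, 0 of 14: 1 − 0.05^(1/14) = 0.193. That trial's DLT definition is not given.

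The two are not pooled because they count different events.

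Planned infusions per subject are 3 courses × 3 days = 9. Those followed by a scheduled next-day dose are 3 × 2 = 6. The conflict needs a related, vasopressor-treated Grade 4 event after one of those 6, with vasopressors off by the next day. The documents do not give the share of such events weaned that fast, so no probability of the conflict is calculated.

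**The case against.** The strongest reply is that both texts can be obeyed. Section (c) only permits, 5.4.4.1 commands, and declining to use a permission breaches nothing. Section 10.2 is headed as supportive care, while the dose rules sit in 5.4 and 10.1. This largely stands: the documents do not support reading the two as instructions that cannot both be followed, and 5.4 should prevail. What survives is that (c) permits an action that would breach a mandatory safety rule, and does not say so.

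A reader might also infer more than the text bears out.
- That (c) is wrong for every vasopressor-treated case. Step 2 shows otherwise.
- That no safeguard leads from (c). For Grade 3 its pointer reaches the FDA-contact rule in 10.1.1, which applies after any DLT. The gap is at Grade 4 only. Section 14.2 also requires Grade 4 events to be phoned to the FDA within 24 hours, though that call need not precede a next-day dose.
- That 10.1.1 is a separate contradiction. It restates the general rule that opens 5.4.4.1 and omits the Grade 4 paragraph, so it needs a cross-reference and no more.
- That the vasopressor sentences in 10.2.3.4 repeat the problem. They resume treatment only after toxicities resolve and grant no next-day restart, so they are peripheral.

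Finally, Section 5.4.4 refers to Figure 1 for continued treatment. The figure is not shown and may already route Grade 4 events. Its absence here is not a fault in the plan, and it limits certainty about whether the gap is closed elsewhere. If the figure does close it, (c) still does not cite it.

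**Conclusion.** The point holds for treatment-related Grade 4 hypotension. Section 10.2.3.2.2(c) leaves open a next-day half-dose restart in a subject whom 5.4.4.1 withdraws, and it neither limits the permission nor refers to the rule that overrides it.

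The event is expected to be rare: none of 33 Phase I subjects had any Grade 4 toxicity, with an upper bound of 8.7% across all doses. It is not fanciful. Section 1.3.5 reports a Grade 4 vascular leak syndrome needing ventilatory support in one of 39 children enrolled at 12.0 mg/m²/d, twice the present dose (12/6 = 2), and 9.4.9 sets a stopping boundary that includes Grade 4 hypotension.

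The conclusion assumes that the mandatory wording in 5.4 expresses the sponsor's intent, and it is subject to what Figure 1 shows. A reader might infer that the trial's inference is compromised. Nothing here supports that: power, alpha and sample size do not depend on this wording. It should be corrected because the remedy is small and the exposure is to subject safety.

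**What to change.** In 10.2.3.2.2(c):
- Limit the restart to hypotension below Grade 4.
- Add: for treatment-related Grade 4 hypotension, give no further hu14.18-IL2 and follow 5.4.4.1 (withdrawal).
- Extend the existing pointer to 10.1 so that any restart after a DLT has the FDA contact first.
- If Figure 1 already routes Grade 4 events, cite it.

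In 10.1.1, add only: subject to the Grade 4 rules in 5.4.4.1. A blanket exclusion of Grade 4 there would be wrong. It would cut across the exceptions listed in 5.4.4.1 and its provision for clearly unrelated Grade 4 events of 3 days or less.

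No change to 10.2.3.4 is essential; a cross-reference to 5.4.4.1 is optional.

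The cost is protocol wording only. The change causes no additional withdrawals, because 5.4.4.1 already requires them.
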